Patients will not be blinded as to what study group they have been randomized to participate in. Blinding of subjects can be beneficial in studies because it minimizes the introduction of biases stemming from awareness. Blinding is not always possible, however. For example, in this study it would be challenging to blind subjects to the sciatic nerve block treatment group, as one group will have an indwelling sciatic CPI catheter and the other will not. One means of blinding study participants would be to insert sciatic CPI catheters in all patients and infuse local anesthetic in one group and a placebo in the other group, however, the costs and potential risks, such as opportunity for infection, potential tissue damage and potential for abscess formation secondary to infusion of a placebo, makes blinding of study participants prohibitive.

1. Sciatic Peripheral Nerve Blockade Description:

Under ultrasound-guidance, the sciatic nerve can readily be identified in the posterior thigh. The nerve appears hyperechoic and can be traced distally to the popliteal fossa, where it divides into the tibial and common peroneal nerves. Local anesthesia is injected under real-time visualization following a negative aspiration. If a single-injection block is done, local anesthesia is deposited adjacent to the sciatic nerve within the fascial plane, but not within the epineurium. Should a CPI catheter be placed, the CPI catheter will be placed under ultra-sound guidance, with the tip of the catheter being placed immediately adjacent to the sciatic nerve, after the local anesthesia has been deposited.

Peripheral Nerve Blockade Related Risks: While the general risks for peripheral nerve blockade apply to femoral and sciatic nerve blockade, the site of injection for these blocks is considered relatively low risk. The risks of the drug in the current study are no different than would be expected when the drug is used in any other local infusion. As with any local anesthetic drug, high doses or unintentional intravascular injection may lead to high plasma levels and related myocardial depression, decreased cardiac output, heart block, hypotension, bradycardia, ventricular arrhythmias, including ventricular tachycardia and ventricular fibrillation, and possibly cardiac arrest.

Risks related to the drug utilized in the current study ropivacaine are characteristic of those associated with other amide-type local anesthetic drugs, which include:

- Urticaria
- Pruritus
- Erythema

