significant differences exist between the outcome measures of each sciatic PNB technique. Performing an interim analysis limits the number of patients exposed to study procedures. If statistically significant differences exist such that one of the two sciatic PNB techniques clearly produces superior patient outcomes, the study will be stopped. However, should the outcomes measures of each sciatic PNB technique be found to be equivalent and without statistically significant differences enrollment will continue.

VII. DATA SAFETY AND MONITORING

Adverse events will be collected until data collection is complete. Adverse events will be recorded on the case report forms. Details will include an explanation of the event, seriousness, anticipation, treatment, resolution and relatedness to the study treatment. All study-related adverse events will be followed through to completion

A. Adverse Event Definitions:

The definitions for adverse event, adverse device effect, serious adverse event, serious adverse device effect, and unanticipated adverse device effect are provided below (ANSI/AAMI/ISO 14155-2:2003, 21 CFR 812.3(s)).

Adverse Event: an adverse event is any untoward medical occurrence in a subject, which need not be related to the treatment under investigation.

Adverse Peripheral Nerve Blockade Blockade Effect: an adverse peripheral nerve blockade effect is any untoward or unintended response to regional blockade, which may result from insufficiencies in the deployment of the ultrasound machine, or from provider error.

Serious Adverse Event: a serious adverse event is an adverse event that results in death, inpatient hospitalization, severe or permanent disability, a life threatening illness or injury, fetal distress, fetal death, a congenital abnormality, a birth defect, or medical or surgical intervention to prevent permanent impairment to body or structure.

Serious Adverse Peripheral Nerve Blockade Effect: a serious adverse peripheral nerve blockade effect is an adverse regional blockade effect that results in death, inpatient hospitalization, and severe or permanent disability or is life threatening.

Unanticipated Peripheral Nerve Blockade Effect: any serious adverse effect on health or safety or any life threatening problem or death caused by, or associated with, peripheral nerve blockade if the effect, problem, or death was not previously identified in nature, severity or degree of incidence in the

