investigational plan, or application (including a supplementary plan or application) or any other unanticipated serious problem associated with peripheral nerve blockade that related to the rights, safety or welfare of subjects. Refer to the Peripheral Nerve Blockade Risk Analysis and Risk Assessment section for details on anticipated adverse regional blockade effects.

B. Adverse Event Reporting:

All serious adverse events will be reported to the IRB per IRB reporting requirements. These reports may include, but will not be limited to: date of onset; brief description of the events; their treatment; whether they resulted in death, inpatient hospitalization, severe or permanent disability or were life threatening; their relationship to the study device; and resolution. All unanticipated adverse device effects will be reported to the IRB.

C. Data Safety Monitoring Plan:

In an effort to ensure patient safety throughout the course of this study, a Data Safety Monitoring Plan has been established. The Data Safety Monitoring Committee shall convene at predetermined intervals to assess the progress of the study for potential patient-related adverse events. Such events include, but are not limited to: infection at the CPI catheter insertion site, infusion pump malfunction, local anesthetic toxicity, skin irritation or allergic reaction secondary to CPI catheter dressings, and falls secondary to motor blockade. Should 2 or more study-related adverse events occur, the study will be suspended immediately pending review of the study and results to date by the Data Safety Monitoring Committee. In addition, should any unforeseen study-related adverse event not previously reported in the literature occur, the study will be stopped for review by the Data Safety Monitoring Committee. Should the study be stopped at any point, enrollment will not resume until the Data Safety Monitoring Committee has determined that it is safe to resume the study. In addition, at any point during the course of the study should the Data Safety Monitoring Committee determine that it is not in the best interest of adolescent patients undergoing ACL with a hamstring autograft to continue the study, the study will be stopped.

D. Data Safety Monitoring Committee:

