The Data Safety Monitoring Committee will meet to review the results of the study to date following the enrollment of the 30 participants, 60 participants, and 90 participants. In addition, the Data Safety Committee shall convene if 2 or more study-related adverse events occur related to this study. The Data Safety Monitoring Committee shall be comprised of 2 members of the Department of Anesthesia credentialed by CCHMC to perform peripheral nerve blockade but who are not part of this study ([name] and [name]), a statistician, and a patient advocate. The patient advocate will be the parent of a patient who has previously undergone ACL reconstruction at the Liberty Campus of CCHMC.

VIII. PRIVACY AND CONFIDENTIALITY

All subjects screened and enrolled in this study will be identified only by their initials and/or assigned study number only. Data confidentiality will be maintained by data being stored in a password protected computer and hard copies of subject information stored in a locked office. All information collected will be treated as confidential, as provided by law. The study records will be made available for review only to the Institutional Review Board (IRB) and the Food and Drug Administration (FDA). The subjects' names or any identifier will not be used in published information relating to this study.

IX. FUNDING

This is a CCHMC investigator initiated study that has received financial support from the AANA Foundation.

X. COST AND PAYMENT FOR PARTICIPATION

The patient's insurance company will be charged for all PNB and associated equipment utilized in this observational study. This is not a departure from standard practice of care, as PNB is routinely employed for postoperative pain control following ACL reconstruction with a hamstring autograft in the adolescent population.

Patients undergoing surgery with [name] will not receive any charges related to PNB as they will not receive PNB per his discretion.

The patient's insurance company may be charged for continuing medical care and/or hospitalization including tests and treatments of any side effects of the study treatment that may occur. In the event that the insurance does not cover all costs, patients may incur additional costs because of treatment side effects.

A \$20.00 gift card will be distributed as incentive to all participants who enroll in this study. The gift card will be mailed upon completion of the data collection process during the three days following surgery.

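### A foreseen serious event, such as a cardiac arrest from the block drug, fires neither safety trigger in VII.C if it is the first study-related event, and no rule requires that the committee be told of it

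*Combined protocol and SAP*

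**What the plan says.** All references are to the combined protocol and SAP.

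- **VII.C, count rule:** "Should 2 or more study-related adverse events occur, the study will be suspended immediately pending review". Severity plays no part. VII.D uses the same count of two for an unscheduled committee meeting.
- **VII.C, single-event rule:** "should any unforeseen study-related adverse event not previously reported in the literature occur, the study will be stopped for review".
- **VII.C, general power:** the committee may end the study at any time if it judges that continuing is not in patients' interest.
- **VII.B:** "All serious adverse events will be reported to the IRB per IRB reporting requirements". No other recipient is named.
- **VII.D:** the committee meets "following the enrollment of the 30 participants, 60 participants, and 90 participants".
- **VII.A:** defines serious and unanticipated block effects. An effect is unanticipated if it "was not previously identified in nature, severity or degree of incidence in the" investigational plan or application.
- **V.A.1:** lists, among the effects of high plasma levels of local anesthetic, "ventricular arrhythmias, including ventricular tachycardia and ventricular fibrillation, and possibly cardiac arrest".
- **V.A.2:** describes the risks of sciatic block as belonging to the block and not to the study.

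**The concern.** A safety plan usually lets one grave event reach the monitoring body without waiting for a second. Here VII.A defines the serious and unanticipated categories, and the opening of VII has seriousness and anticipation recorded on the case report forms. The VII.C triggers then make no use of seriousness, and they replace the VII.A test for unanticipated events with a narrower one. Followed exactly, the rules can leave the committee unaware of a first life-threatening event while enrollment continues.

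The participants are outpatients aged 10 to 18, with one or two ropivacaine infusions running for 48 hours after surgery. What is at stake is the time between such an event and its review by the body set up for that purpose.

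**Working it through.** **1. One event taken through the rules.** Suppose a cardiac arrest from local anesthetic toxicity is the first study-related event.

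| Rule | Requirement | Met? |
|---|---|---|
| VII.C count rule | 2 or more study-related events | No, the count is 1 |
| VII.C single-event rule | unforeseen, and not previously reported in the literature | No, V.A.1 names it |
| VII.D unscheduled meeting | 2 or more study-related events | No, the count is 1 |
| VII.B report | serious event | Yes, to the IRB |
| VII.D scheduled meeting | after 30, 60 or 90 participants | Only if one is still to come |

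The single-event rule joins its two conditions, so failing one is enough.

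**2. VII.A against VII.C.** VII.A asks whether the plan identified the effect. VII.C asks in addition whether the literature has reported it. A serious effect absent from the plan but published once is unanticipated under VII.A, yet does not fire the single-event stop in VII.C.

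**3. Patients after the last scheduled meeting.** V.D gives 140. That figure reproduces: a two-sample t-test with effect size 0.5, two-sided alpha 0.05 and power 0.80 needs 63.8, so 64 per group. The plan raises this to 70 (70/64 = 1.094), and 2 × 70 = 140. Then 140 − 90 = 50, and 50/140 = 35.7%.

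**4. How often an earlier event closes the gap.** If any study-related event has already occurred, a first serious event is the second event and the count rule suspends the study. Let p be the chance that a patient has any study-related event. The documents give no rate, so p is assumed. With independent patients and a running count, the chance of no event before patient k is (1 − p)^(k − 1). For example, at p = 1% and k = 30 it is 0.99^29 = 0.747. The last column averages the formula over k = 91 to 140.

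| Assumed p | Patient 30 | Patient 91 | Average, patients 91–140 |
|---|---|---|---|
| 0.5% | 0.865 | 0.637 | 0.565 |
| 1% | 0.747 | 0.405 | 0.320 |
| 2% | 0.557 | 0.162 | 0.103 |
| 5% | 0.226 | 0.010 | 0.004 |

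The count rule is most likely to be silent early, when a scheduled meeting is still ahead. After participant 90 no meeting is scheduled, but the count rule is silent only if events are rare.

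**5. What counts as study-related.** V.A.2 sets block risks apart from the study. The opening of VII has relatedness judged against the study treatment, and the examples in VII.C are block and catheter complications. On the V.A.2 reading, a block injury might count toward neither trigger, and the gap is wider than step 4 shows.

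**The case against.** The strongest defense is that a two-event rule blind to severity is cautious. One earlier minor event is enough to make a first serious event suspend the study at once, at any stage. In addition, every serious event goes to the IRB, and the committee can stop the study whenever it sees fit. The first part stands and limits the finding, as step 4 shows. The other two do not close the gap. Reporting to the IRB does not inform the committee, and a power to stop is of use only once the committee knows of the event. VII.B does not say that the IRB is the sole recipient, so the absence of a route to the committee is read from silence. Still, no section supplies one.

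V.A.1 also uses the word unforeseen to introduce a list that includes local anesthetic toxicity. On that label an arrest from toxicity might be called unforeseen. It would then also have to be new to the literature, and V.A.1 presents it as an effect of local anesthetics in general. The label is one more term to reconcile.

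A reader might infer more than the documents support:

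- *That a first death or permanent injury also fails the single-event rule.* Neither is in the risk lists of V.A.1, and whether the literature has reported them after a block needs outside sources. Failure is shown only for cardiac arrest. For the same reason, the documents do not show that the single-event stop is practically empty.
- *That a serious event after participant 90 reaches the committee only if a second event follows.* An earlier event of any severity is enough.
- *That the gap is the same however study-related is read.* It is not, because of V.A.2. Nor can it be taken as settled that two dressing irritations would suspend the study, since they might not count as study-related.
- *That the delay can be stated in months.* That needs even accrual, and the plan gives only about two years to enroll and complete.

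**Conclusion.** The point holds in a limited form. A foreseen serious event that is also the first study-related event fires neither VII.C trigger. The only written report goes to the IRB, and no committee meeting is scheduled for the last 50 of 140 planned patients.

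The size depends on how common study-related events are. Over the assumed range of 0.5% to 5% per patient, the count rule would be silent with probability 0.865 to 0.226 for an event at patient 30, and 0.565 to 0.004 on average over patients 91 to 140. These figures assume independent patients, a constant rate, and a count that is not restarted after a review, on which VII.C is silent. They are conditional on a serious event happening and say nothing about how likely one is.

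The 50 assumes exactly 140 enrolled. V.D allows extra subjects, and VII.D does not say whether the no-block comparison patients in V.B count as participants. Either would put more than 50 randomized patients after the last meeting.

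This is more than missing detail, because the stated rules, followed exactly, can leave the committee uninformed. It is a worthwhile, inexpensive correction and does not affect the sample size or the analysis.

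**What to change.** Reconcile VII.A to VII.D with V.A.1 and V.A.2:

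1. State that block-related and catheter-related events count as study-related for VII.C.
2. Send the first event that is fatal, life-threatening, or severely or permanently disabling, or that meets the VII.A definition of unanticipated, promptly to the existing committee as well as the IRB. Let the committee decide whether enrollment pauses.
3. Use the VII.A standard in VII.C in place of the literature test, and use the word unforeseen consistently with it.
4. Keep the count rule for other events, and say whether the count restarts after a review.

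The cost is protocol wording, an occasional unscheduled meeting of a committee that already exists, and a possible short pause in enrollment after one serious event.

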Appendix A
Preoperative Data Collection Instrument

PATIENT STUDY ID NUMBER: _____

Age (in years) on day of recruitment: _____

Gender (circle one): Male Female

BMI: _____

ASA physical status (circle one): I II

Previous surgery: Yes No

If yes, what surgery? _____

Self-reported preoperative pain score (0 = no pain, 10 = worst pain): _____

Self-reported tolerance of pain (circle one):

0 = Low tolerance of pain

1 = Moderate tolerance of pain

2 = High tolerance of pain

Self-reported level of activity since the time of ACL injury (circle one):

0 = Not active at all

1 = Not active

2 = Partially active

3 = Active

4 = Highly active

What is your level of anxiety today (0 = no anxiety, 10 = worst anxiety): _____

- Are you normally anxious (yes/no)? _____
- Do you take any prescriptive medications for anxiety (yes/no)? _____
- Are you currently, or have you in the past, seen a healthcare professional for treatment of your anxiety (yes/no)? _____

[name]

Appendix B

Post-Discharge Data Collection Instrument

PAIN CONTROL:

Keep track of your pain score and location of pain:

Pain score: 0 = no pain, 10 = worst pain			
Pain location: F = front of knee, B = back of knee, X = both front & back			
6 hours		42 hours	
12 hours		48 hours	
18 hours		54 hours	
24 hours		60 hours	
30 hours		66 hours	
36 hours		72 hours	

Date and time the leg was no longer numb behind the knee: _____

Pain medicine prescribed (circle one): Vicodin Percocet Other: _____

Write down every time pain medication is taken:

[illegible]

ACTIVE KNEE MOVEMENT:

Rate the ability to bend the knee that was operated on:

Knee Movement	12 hours	24 hours	36 hours	48 hours	60 hours	72 hours
0 = Able to bend with no pain						
1 = Able to bend, but with pain						
2 = Too much pain to bend						

SATISFACTION:

Rate your overall satisfaction score with pain management:

Satisfaction Score	12 hours	24 hours	36 hours	48 hours	60 hours	72 hours
0 = Not satisfied at all						
1 = Not satisfied						
2 = Partially satisfied						
3 = Satisfied						
4 = Highly satisfied						

From your perspective, have you encountered any unexpected postoperative experiences?

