There is evidence that sciatic PNB, regardless of technique, significantly reduces pain when compared to intravenous opioids during the initial 24-hour postoperative period following knee surgery (Wegener, van Ooij, van Dijk, Hollmann, Preckel, & Stevens, 2011). As such, single-injection sciatic PNB, which can last up to 24 hours, should provide adequate analgesia precluding the need for oral narcotic or nonsteroidal anti-inflammatory medications following ACL reconstruction with a hamstring autograft. It remains unknown, however, if any benefit is gained during the initial 72-hour postoperative period from extending analgesia for the hamstring donor site via continuous sciatic PNB. While continuous sciatic PNB with a CPI catheter extends the duration of analgesia, it also extends the duration of anesthesia potentially leading to a decrease in motor function and subsequently active knee flexion. The sciatic nerve innervates the hamstrings, which are responsible for knee flexion (Distad &

Weiss, 2013). The decrease in active knee flexion may impede the ability of the patient to begin rehabilitation on the first postoperative day. This is an important consideration because early rehabilitation, which includes contraction of the quadriceps and hamstring muscles as well as weight bearing exercises with the aid of crutches, leads to faster recovery of long-term range of motion and a lower incidence of knee laxity following ACL reconstruction when compared to delayed rehabilitation (Shaw, Williams, & Chipchase, 2005; Pinczewski et al., 2007). Determining the duration of sciatic PNB required to effectively control pain following ACL reconstruction with a hamstring autograft, without impeding active knee movement, will help define best practice going forward.

II. RESEARCH QUESTION

This study aims to answer the following research question: Does the duration of sciatic PNB impact the ability to effectively provide postoperative pain control following ACL reconstruction with a hamstring autograft in the adolescent population?

III. PURPOSE OF THE STUDY

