The intervention in this study will be one of two techniques for sciatic PNB: single-injection PNB or continuous sciatic PNB with a CPI catheter. The PNB protocol will be assigned by computer-generated randomization. All study participants will receive standard care, including standard anesthetic care as recommended by the American Society of Anesthesiologists and the American Association of Nurse Anesthetists, and the surgical procedures will be in accordance with those set forth by the American College of Surgeons. Anesthetic management will be left to the discretion of the clinical team providing anesthesia care, which includes, but is not limited to, the amount of inhalation anesthetic and intravenous opioids each study participant receives throughout the intraoperative portion of the study.

All sciatic PNB will be performed following the induction of general anesthesia, but prior to the end of anesthesia. For patients randomized to the single-injection sciatic PNB group, ultrasound will be utilized to identify the sciatic nerve in the sub-gluteal region. Once the sciatic nerve is identified, 1 mL/kg (to a maximum volume of 20 mLs) of 0.2% ropivacaine without epinephrine will be injected into the perineural space surrounding the sciatic nerve.

For patients randomized to the continuous sciatic PNB group, ultrasound will be utilized to assist the anesthesia team with placing the catheter tip adjacent to the sciatic nerve in the sub-gluteal region in preparation for continuous infusion of local anesthetic postoperatively. Once proper placement of the sciatic CPI catheter is verified, 1 mL/kg (to a maximum volume of 20 mLs) of 0.2% ropivacaine without epinephrine will be administered incrementally over two minutes. An infusion of 0.125% ropivacaine will be started at the end of surgery at a rate of 3-4 mL/hr (based on patient weight) for 48 hours postoperatively. While assessments will be made through 72 hours postoperatively, CPI catheters will only remain in-situ for 48 hours, as the incidence of infection increases should an indwelling CPI catheter remain greater than 48 hours (Jeng, Torrillo, & Rosenblatt, 2010).

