- Angioneurotic edema
- Tachycardia
- Sneezing
- Nausea
- Vomiting
- Elevated temperature
- Possibly anaphylactoid symptomology

Additionally, there is a low risk of mild discomfort or inconvenience to the subject, as they will receive regional blockade of some nature. Additionally, unforeseen risks may include, but are not limited to:

- Needle trauma
- Intraneural injection
- Intravascular injection
- Local anesthetic toxicity
- Hematoma
- Infection
- Poor/failed block

Finally, risks related to the use of a CPI catheter are rare, but include:

- Infection
- Infusion pump malfunction
- Local anesthetic toxicity
- Skin irritation or allergic reaction secondary to dressing material
- Unintentional CPI catheter dislodgement

- Fluid (local anesthetic) leakage at the CPI catheter insertion site
- Falls secondary to motor blockade

2. Risk Benefit Analysis:

Benefits: Subjects in this research study are unlikely to gain any personal benefit on the day of the study from their participation as the decisions of the clinical team caring for the patients will be guided by the randomized study protocol. The knowledge gained may be of benefit in the management of future adolescent patients who require ACL reconstruction. The ability to effectively provide pain control will lead to more efficient utilization of healthcare resources.

Study Related Risks: The risks associated with this study are minimal and are related to PNB. Both techniques of sciatic PNB included in this study are accepted techniques in clinical practice. All risks related to sciatic PNB are incidental, that is, associated with PNB, not the study itself as this is an observational study.

Risks/Benefit Analysis: It is the opinion of the principal investigator (PI) that this study is classified as “minimal risk but without direct benefit to participants”.

B. Subject Population:

A subject may be INCLUDED in this study if:

1. The subject is male or female;
2. The subject is of any racial or ethnic group;
3. The subject is age 10 years to 18 years (inclusive);
4. The subject is scheduled for the following:
Unilateral ACL reconstruction with a hamstring autograft under general anesthesia on an outpatient basis, and not being performed in conjunction with any other surgical procedures;
5. The subject is American Society of Anesthesiologists (ASA) patient classification I-II;

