date and time their leg was no longer numb behind their knee. The orthopedic surgeon performing the ACL reconstruction or a member of his orthopedic team will prescribe all postoperative oral pain medication. The oral pain medication typically prescribed is either Percocet or Vicodin. Vicodin, a schedule 3 controlled substance, is approximately half as potent as Percocet, which is a schedule 2 controlled substance. The patient will record the time and dose of all oral pain medication taken during the 72 hours postoperative period. The patient or their guardian will also record data regarding pain associated with active knee flexion once every 12 hours for 72 hours postoperatively. In addition, the patient or their guardian will record satisfaction with pain control once every 12 hours for 72 hours postoperatively.

The research coordinator may collect all data recorded by the patient and/or their guardian via telephone interview. Data will be collected using the same data collection tool given to the study participants to avoid instrumentation and maintain interrater reliability. Untoward events, such as unplanned hospital admission, CPI catheter dislodgement, or local anesthetic toxicity, will also be noted should they occur. This information will be collected from the patient or guardian once every 24 hours by the research coordinator during the 72-hour postoperative period; the postoperative period begins at the time of discharge from the PACU.

1. Survey(s) and Questionnaire(s):

Patients and their guardian will be given data collection instruments to complete postoperatively at the time of enrollment to facilitate recall when conveying information to the study staff during telephone conversations. The data collection instruments will be available in different languages and utilized for non-English speaking patients and/or guardians. The patient and their guardian(s) will receive training regarding the data collection tool both during the time of enrollment and again prior to discharge from the hospital. At the time of enrollment, essential phone numbers, including home phone and cell phone numbers, will be collected. Should the patient and/or guardian lose the data collection sheet, additional copies can be emailed to them upon request. Hospital-approved interpreters will be utilized for non-English speaking patients and/or guardian(s).

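### The diary's numbness item cannot record numbness that has not ended by 72 hours, so persistent numbness could look the same as missing data

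*Combined protocol and SAP*

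**What the plan says.** - **Numbness item.** Section V.G has the patient or guardian note the "date and time their leg was no longer numb behind their knee". Appendix B prints this as a single free-entry line, "Date and time the leg was no longer numb behind the knee". Neither place provides for numbness that has not ended.
- **Intended block duration.** Section I describes "single-injection sciatic PNB, which can last up to 24 hours". For the continuous arm, Section V.A says that "CPI catheters will only remain in-situ for 48 hours".
- **End of collection.** Diary entries and daily calls run to 72 hours after surgery (Sections V.G and V.H). Section VII adds: "Adverse events will be collected until data collection is complete".
- **Risks named.** The list of block risks in Section V.A.1 includes needle trauma and "Intraneural injection". It does not name nerve injury or lasting numbness.
- **Other reporting routes.** The coordinator contacts the family every 24 hours, and Section V.G says: "Untoward events, such as unplanned hospital admission, CPI catheter dislodgement, or local anesthetic toxicity, will also be noted should they occur". Appendix B closes with an open question: "From your perspective, have you encountered any unexpected postoperative experiences". The definitions of an adverse event and of an adverse block effect in Section VII.A are broad. Section VII says that adverse events go on case report forms and that study-related ones are followed to their conclusion.
- **Analysis.** None of the analyses in Section VI.B uses the time at which numbness ended.

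**The concern.** The trial compares one injection with 48 hours of perineural infusion, so sensory loss that outlasts the intended block is a relevant comparative safety outcome. The one item that asks about sensation records only when numbness ended. The patients of most interest, those in whom it has not ended, have nothing to enter. Their forms could then match those of patients who were never numb or who skipped the line. Because VI.B makes no use of the item, no planned analysis would bring the blanks to light. Once the last call has passed, an analyst cannot recover what a blank meant. At stake are a fair by-arm account of persistent numbness and what the Data Safety Monitoring Committee sees at its reviews after 30, 60 and 90 participants.

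**Working it through.** The plan states no figure for numbness, so there is nothing to reproduce. The check is a comparison of sections plus illustrative arithmetic.

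**1. Does 72 hours lie beyond both intended blocks?**
- Single injection: 72 − 24 = 48 hours past the longest stated duration (Section I).
- Continuous: 72 − 48 = 24 hours past the planned end of infusion (Section V.A). This is approximate, because V.G starts the postoperative clock at discharge from the recovery unit while V.A starts the infusion at the end of surgery.

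The femoral infusion given to both arms is also planned for 48 hours. A question at 72 hours therefore has the same meaning in both arms and does not require the coordinator, whom Section V.E keeps blinded, to know the assignment.

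**2. What can a blank mean?** There are three possibilities: still numb, never numb, or not recorded. No section gives a coding rule. For scale, Section V.D enrols 70 per group against 64 needed, an allowance of 70 − 64 = 6 for attrition and lost data. Suppose, as an illustration only, that 6 numbness times in an arm are blank. The proportion still numb could then lie anywhere from 0/70 = 0% to 6/70 = 8.6%.

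**3. Do the other routes ask about sensation?**

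| Route | Place | Specific to sensation? |
|---|---|---|
| Daily enquiry on untoward events | V.G | No; open list, numbness not among the examples |
| Open question on the unexpected | Appendix B | No; numbness is expected after a block, so a family may not mention it |
| Knee-movement scale | Appendix B | No; graded only by pain on bending |
| Events named for the safety committee | VII.C | No; open list, nerve injury and numbness not named |
| General adverse-event definitions | VII.A | Would cover it, once someone reports it |

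**4. How many patients might be involved?** The rates p below are assumptions; nothing in the documents anchors them. With 140 patients, the expected number is 140 × p, and the chance of at least one is 1 − (1 − p)^140. The chance of at least two is 1 − (1 − p)^140 − 140p(1 − p)^139.

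| Assumed p | Expected cases | At least one | At least two |
|---|---|---|---|
| 0.5% | 0.7 | 50% | 16% |
| 1% | 1.4 | 76% | 41% |
| 2% | 2.8 | 94% | 77% |
| 5% | 7.0 | >99.9% | 99% |

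The last column matters for the form of the fix, because VII.C suspends the study once two study-related adverse events have occurred.

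**5. What could the trial report if the item were answered?** With 0 of 70 still numb in an arm, the upper limit of an exact two-sided 95% interval is 1 − 0.025^(1/70) = 5.1%. That is a modest statement, but one the present form does not allow.

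**The case against.** The strongest reply is that the protocol already has a safety net. The coordinator asks about untoward events every day to 72 hours, the diary has an open question, and numbness well past the intended block fits the definitions in VII.A. Study-related events are then recorded and followed to their conclusion. The field is free entry, so a patient can write that the leg is still numb, and a coordinator going through the same tool by telephone can query a blank. The case report forms are not among the documents, so their content cannot be judged. The tool is also to be piloted and revised.

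Much of this stands, and it rules out several stronger readings:
- A reader might infer that persistent numbness would be neither recorded as an adverse event nor followed, and so would go unreported. The documents do not support that. They support only that it could be missed, because nothing leads from the diary item to the adverse-event process.
- A reader might call the item the only patient-reported sign of nerve injury. It is the only specific sensory item. Other patient-reported routes exist, and the protocol nowhere describes the item as a screen for nerve injury.
- A reader might call persistent numbness a listed harm. Section V.A.1 lists possible mechanisms, not the outcome.
- A reader might say that the committee would not see such cases. Its event list is open and it reviews results to date, so the most that can be said is that it might not.

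What does not stand is that the general routes make the item adequate. They depend on a family volunteering something they were told to expect, or on a coordinator choosing to probe. The pilot has five volunteers: even at an assumed 5%, the chance that it meets one unresolved case is 1 − 0.95^5 = 23%.

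**Conclusion.** The point holds as a gap in form design and safety linkage. The numbness item has no entry for numbness unresolved at 72 hours, no coding rule for a blank, and no stated route to adverse-event assessment. Persistent numbness could therefore be indistinguishable from missing data. This rests on the text alone and needs no assumed rate.

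Its size is unknown. The range of 0.7 to 7 cases among 140 follows entirely from the assumed 0.5% to 5%, and some of those cases would be ordinary late resolution of the block. The general safety routes would catch some, and the documents do not show how many. The change is worth making because it is cheap and the information cannot be recovered afterwards, not because a large number of cases has been shown.

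**What to change.** 1. **Appendix B:** beside the resolution time, add *still numb behind the knee at 72 hours: yes / no*, and ask it at the existing day-3 call.
2. **Section VII:** state that a yes is passed to the investigator for assessment under the existing definitions, including relatedness, with study-related events followed to their conclusion as already promised.
3. **Section VI.B:** report the number still numb at 72 hours by arm, with an exact 95% confidence interval and the number of patients who answered. In any summary of time to resolution, treat unresolved times as censored at 72 hours rather than missing. Patients not reached on day 3 remain missing and should be counted as such.

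The fix should not make every yes an adverse event automatically. That would set a clinical threshold feeding directly into the VII.C suspension rule. If every case were also judged study-related, the assumed rates above give a 16% to 99% chance of reaching two. Whether and when a yes counts as an adverse event, and how that fits with VII.C, is for the protocol author to decide.

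The cost is one tick box, a sentence in VII, a short addition to VI.B, and a few extra calls by the existing coordinator. The downside is that some ordinary late resolution will be sent for assessment.
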